11.2 Deriving and Summarizing Pharmacokinetic Parameters

PK parameters will be derived using non-compartmental PK analyses and will be summarized descriptively by dosing regimen (i.e., 100 mg Q2M, 100 mg Q1M).

The following descriptive statistics will be presented for all PK parameters, except for T_{\max} : number of observations (for definition see [Section 11.1](#)), mean, SD, CV%, median, minimum, and maximum, geometric mean, geometric CV% (for definition see [Section 11.1](#)). For T_{\max} , number of observations, median, minimum, and maximum will be provided.

By-subject listings will be provided for the PK parameters.

12 Pharmacodynamic and Biomarkers Analyses

All analyses in this section will be based on the PD Analysis Set.

12.1 Pharmacodynamic Analyses

FXIIa-mediated kallikrein activity and FXII concentrations will be summarized by nominal time point and dosing regimen (i.e., 100 mg Q2M, 100 mg Q1M). The following descriptive statistics will be provided: number of observations (values \geq LLOQ plus BLQ values), number and percentage of BLQ values, mean, SD, CV%, median, minimum, maximum, and Q1 and Q3, geometric mean and its respective 90% CI, and geometric CV% (for definition see [Section 11.1](#)).

Mean (\pm SD) concentration/activity-time profiles will be plotted using nominal (planned) time. Individual concentration/activity-time plots will be presented by actual sampling time point.

By-subject listings will be provided for FXIIa-mediated kallikrein activity and FXII concentration including actual sampling date and time, nominal time point and actual time from end of previous injection.

For FXIIa-mediated kallikrein activity, % of Baseline values will be provided in the listings and summaries. For calculation of % of Baseline values see [Section 7.2.4](#).

BLQ results will not be considered for summaries and will only be listed.

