During acute HAE attacks, bradykinin (BK) production is increased and is the mediator of swelling in HAE [Nussberger et al, 1998; Nussberger et al, 1999]. Acute and prophylactic treatments for HAE are based on blocking BK production through targeting different proteins in the kallikrein kinin pathway. Plasma levels of FXIIa have been shown to increase in patients during acute HAE attacks compared to levels during remission [Csuka et al, 2015; Cugno et al, 1996]. Given the importance of FXIIa in the initiation of the plasma contact system, it is a novel target for the inhibition of the kallikrein kinin pathway and the excessive production of BK detected during HAE attacks.

The rationale for evaluating CSL312 for prophylaxis to prevent HAE attacks relies on the strong inhibition of FXIIa catalytic activity by CSL312 resulting in the upstream blocking of the contact pathway that produces BK, which feeds the central pathogenic mechanism of HAE.

The efficacy and safety of CSL312 in adult patients with HAE has been demonstrated in a phase 2 study and in a phase 3 study in adult and adolescents with HAE. This phase 3b study is designed to evaluate the safety, pharmacokinetic (PK) / pharmacodynamic (PD), and efficacy of CSL312 in pediatric subjects with HAE (2 to 11 years of age).

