#### **9.4.5. Pharmacodynamic Analyses**

PD data will be summarized using the PD Analysis Set. FXIIa-mediated kallikrein activity and FXII concentration will be listed by individual subjects and will be summarized by nominal time point and dosing regimen (ie, 100 mg Q2M, 100 mg Q1M). The PD data will be summarized with descriptive statistics: n, number and percentage of values below the limit of quantification, mean, SD, CV%, median, minimum, maximum, first and third quartiles for continuous variables, geometric mean and its respective 90% CI, and geometric CV%.

Additional information on the analyses of PD will be provided in the SAP.

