	FXIIa-mediated kallikrein activity at scheduled time points	Descriptive summaries by nominal time point and the percentage of Baseline value
Exploratory		
The exploratory objective of the study is to further evaluate the PD effects of CSL312.	FXII concentration at scheduled time points	Descriptive summaries by nominal time point

C_{max} = maximum plasma concentration; C_{trough} = trough plasma concentration; C1-INH = C1-esterase inhibitor; FXIIa = activated factor XII; HAE = hereditary angioedema; PD=pharmacodynamic; PK = pharmacokinetic; SC = subcutaneous; T_{max} = time to reach maximum plasma concentration.

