11.1 Drug Concentration Measures

Handling of PK concentration data and imputation of below limit of quantification (BLQ) values for noncompartmental analyses will be performed according to the CSL guideline for conducting non-compartmental pharmacokinetic analysis. Plasma concentrations of CSL312 will be summarized by nominal time points and dosing regimen (100 mg Q2M and 100 mg Q1M). Plasma concentrations will be summarized with descriptive statistics: number of observations, i.e., values $>$ lower limit of quantification (LLOQ) plus values below limit of quantification (BLQ), number and percentage of BLQ values, with percentage BLQ values being calculated as $100 * \text{number of values BLQ} / \text{number of observations}$, mean, SD, CV%, median, minimum, maximum, Q1 and Q3, geometric mean and its respective 90% CI, and geometric CV%.

The geometric statistics will be using (natural) log-transformation of the plasma concentration data. The CV% will be expressed as a percentage. It will be calculated as $100 * \sqrt{\exp(\text{SD}_{\log}^2) - 1}$ with SD_{\log} being the SD of the log-transformed data. The geometric mean and its two-sided 90% CI will be calculated as the arithmetic mean and the lower and upper limits of the two-sided 90% Wald CI of the log-transformed data, and subsequently back-transforming the mean and the lower and upper confidence limits.

For summary statistics, calculation of mean concentrations at any individual time points are performed if at least 50% of the individual values are available with measurement values $>$ LLOQ (i.e., are quantifiable); else reports as NC.

The imputation rules below will be used for summary statistics of CSL312 plasma concentrations.

- The sampling time of pre-dose samples relative to start of the dose will be treated as 0.
- Concentration values below LLOQ in pre-dose samples and in samples taken before the time of the first quantifiable concentration will be treated as 0.
- Post-dose BLQ concentrations flanked by quantifiable concentrations will be set to missing.
- If 2 or more BLQ concentrations occur in succession, the profile will be considered to have terminated the quantifiable concentration prior to the 2 consecutive BLQs. All subsequent values will be treated as missing.
- Post-dose BLQ concentrations after the last quantifiable point will be set to missing for summary statistics of plasma concentrations.
- Mean or median values of 0 will be included in summary tables.

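### SAP 12.1 counts below-limit PD values in n but leaves them out of the summary statistics, which understates kallikrein inhibition whenever such values occur

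*SAP*

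**What the plan says.** SAP 3.1 (Table 2) lists "FXIIa-mediated kallikrein activity at scheduled time points" as a secondary endpoint, with the summary measure "Descriptive summaries by nominal time point and the percentage of Baseline value". FXII concentration is exploratory.

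For both variables, SAP 12.1 defines the number of observations as quantifiable values plus BLQ values. The statistics it lists include "LLOQ plus BLQ values), number and percentage of BLQ values, mean, SD, CV%, median, minimum, maximum, and Q1 and Q3", followed by the geometric mean with its 90% CI and the geometric CV%. It adds: "For FXIIa-mediated kallikrein activity, % of Baseline values will be provided in the listings and summaries". The section then ends: "BLQ results will not be considered for summaries and will only be listed".

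Protocol 9.4.5 asks for "n, number and percentage of values below the limit of quantification, mean, SD, CV%, median" and further statistics. It mentions no exclusion of BLQ values, although it leaves further PD detail to the SAP. SAP section 4 says that no changes from the protocol's analyses are planned.

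For drug concentrations, SAP 11.1 has two things that 12.1 lacks: rules for replacing BLQ values, and a rule that a mean is shown only when at least half of the values at that time point are quantifiable. One of its replacement rules says that after two or more BLQ values in a row the profile is taken to have ended: "All subsequent values will be treated as missing".

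**The concern.** The case for using CSL312 in prophylaxis "relies on the strong inhibition of FXIIa catalytic activity by CSL312" (Protocol 2.1). For kallikrein activity, then, a BLQ result is the strongest response the assay can register, not a failed measurement. A rule that drops such results selects on the outcome: the values left out are the lowest ones, so what remains shows less inhibition than the children had.

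The two statements in 12.1 cannot both be followed literally. A programmer has to choose, and the plan does not say how. The choice affects every location and spread statistic for the endpoint, and the mean profile plots too if they use the same values. With about 20 children split over two regimens, a few BLQ results at one visit can move a summary. If the BLQ share differs between regimens or between sampling times, so does the distortion.

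**Working it through.** **Which reading is workable.** If BLQ results appeared only in listings, their number and percentage could not be tabulated, and both documents require that. The reading that satisfies most of the text is that BLQ values enter n, the BLQ count and the BLQ percentage, and nothing else. The printed n is then too large for the statistics beside it. For illustration, with ten children at a visit and three BLQ, the table shows n = 10, but the mean and the CI rest on 10 − 3 = 7 values.

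**Direction, without a model.** Let L be the assay limit. Every BLQ value is below L and every quantifiable value is at least L. Setting BLQ values to L can only raise them, so the resulting mean or geometric mean is an upper bound on the true one. Dropping them raises it at least as far again, because the values kept are all at or above L. Dropping therefore lands at or beyond the most cautious substitution possible.

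**Size, under assumptions.** The plan states no PD effect, assay limit or BLQ share, so there is no figure to reproduce. Assume lognormal activity with geometric CV 30–100%, BLQ share p from 5% to 50%, and a common Baseline, so that activity and percentage of Baseline scale together. With s = √ln(1 + CV²), a = z(p), φ and Φ the standard normal density and distribution function:

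- geometric mean, reported/true = exp[s·φ(a)/(1 − p)]
- median, reported/true = exp[s·z(p + (1 − p)/2)]
- mean, reported/true = [1 − Φ(a − s)]/(1 − p)

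Worked case, CV 50% and p = 30%: s = √ln 1.25 = 0.472; a = −0.524; φ(a) = 0.348.

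- Geometric mean: exp(0.472 × 0.348/0.70) = 1.26
- Median: exp(0.472 × z(0.65)) = exp(0.472 × 0.385) = 1.20
- Mean: [1 − Φ(−0.997)]/0.70 = 0.841/0.70 = 1.20

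A true 10% of Baseline is then reported as 12.6% (90% inhibition shown as 87.4%), and a true 30% as 37.9%.

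Inflation across CV 30–100%:

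| BLQ share | Geometric mean | Median | Mean |
|---|---|---|---|
| 0% | none | none | none |
| 5% | ×1.03–1.09 | ×1.02–1.05 | ×1.02–1.05 |
| 10% | ×1.06–1.18 | ×1.04–1.11 | ×1.05–1.09 |
| 30% | ×1.16–1.51 | ×1.12–1.38 | ×1.13–1.30 |
| 50% | ×1.26–1.94 | ×1.22–1.75 | ×1.23–1.59 |

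**Alternatives.** Simulation with n = 20, CV 50%, 20,000 runs, true geometric mean and median 1.00:

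| BLQ share | Geometric mean, BLQ dropped | Geometric mean, LLOQ/2 | Median, BLQ dropped | Median, BLQ ranked lowest |
|---|---|---|---|---|
| 10% | 1.10 | 0.96 | 1.07 | 1.01 |
| 30% | 1.27 | 0.90 | 1.21 | 1.01 |
| 50% | 1.46 | 0.86 | 1.40 | 1.06 |

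Results at n = 10 are close to these. The ranked median is nearly unbiased while fewer than half of the values are BLQ. LLOQ/2 errs the other way. In percentage terms, with a true 20% of Baseline, CV 50% and a limit at 15% of Baseline (27% BLQ), dropping gives 24.8%, substituting LLOQ gives 21.6% and LLOQ/2 gives 17.9%. The two substitutions bracket the truth here; dropping lies outside the bracket.

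**PK rules in 11.1.** Samples at successive scheduled visits are months apart, with doses in between (Protocol 1.3.1 and 1.3.2). A BLQ trough after the first dose fits the pre-dose rule (set to 0) and also the post-dose rules (set to missing). The text does not say whether a profile means one dosing interval or a child's whole series. On the second reading, two BLQ troughs in a row would discard quantifiable values obtained after later doses.

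**The case against.** The strongest reply is that little is hidden. The table shows how many values are BLQ at each time point, the values themselves are listed, the trial is small enough to read the listing, no test is planned, and the error runs against the drug. PD is not a primary endpoint. All of that stands and limits the severity. It does not make the printed geometric mean or its CI right, and it does not reconcile the two sentences.

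Several stronger readings are tempting, but the documents do not support them:

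- That BLQ values vanish from every summary. Their number and share are tabulated under both documents.
- That the best responders are removed. One PD measurement keeps a child in the PD Analysis Set (SAP 5.6); only the BLQ value at that time point is left out.
- That the PD effect will be understated. Without a PD assay limit or a BLQ share, the bias may be nil. The only limit whose source is named, in SAP 11.1, is for the CSL312 concentration assay.
- That FXII concentration suffers in the same way. The documents state no direction of drug effect for it.
- That the rules in 11.1 push mean trough upward. A BLQ trough set to 0 pulls the mean down, and the half-quantifiable rule may suppress the mean altogether. The primary PK parameters come from a noncompartmental analysis whose BLQ handling follows a sponsor guideline outside these documents.

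It is also fair to object to plain LLOQ/2 as the remedy. It reverses the bias in the drug's favour, and a child BLQ at both Baseline and a later visit would show 100% of Baseline, that is, no inhibition.

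**Conclusion.** The point holds for kallikrein activity. SAP 12.1 is internally inconsistent, and on its workable reading the summary statistics are cut off from below, which understates inhibition whenever any BLQ value occurs. The direction needs only the drug's mechanism and the arithmetic of leaving out the lowest values. The size rests on assumed lognormal activity, CV and BLQ share: a few per cent on the geometric mean at 5% BLQ, roughly a sixth to a half at 30%, and a quarter to almost double at 50%. The mismatch between n and the statistics arises at any BLQ share above zero. This should be fixed, but it does not block the study: the endpoint is secondary and descriptive, and the BLQ counts remain visible. The PK wording is a smaller matter of ambiguity, with no established direction of bias.

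**What to change.** Replace the last sentence of SAP 12.1, for kallikrein activity, with rules to this effect:

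- BLQ values stay in the summaries and rank below all quantifiable values. A median, quartile or minimum that falls below the limit is shown as '<LLOQ'.
- The mean and geometric mean come from a censored-likelihood method, or are shown side by side with BLQ set to LLOQ/2 and to LLOQ. They are reported as not calculated when fewer than 50% of values are quantifiable, in line with 11.1.
- The number of quantifiable values is printed beside n.
- Percentage of Baseline is missing when Baseline is BLQ. When only the visit value is BLQ, it is known only to lie below 100 × LLOQ/Baseline, a limit that differs by child, so both substitutions should be carried through the ratio.

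Section 12.1 should also say which rule FXII concentration follows; the argument here does not settle that.

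In SAP 11.1, limit the rule on two consecutive BLQ values to samples within one dosing interval, so that quantifiable concentrations after later doses stay in the by-time-point summaries. State whether a BLQ trough after the first dose is set to 0 or to missing.

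The cost is a few sentences of SAP text, a little more programming and a conventional substitution value, with the LLOQ version as the upper bound on activity. It should be done before database lock, because a choice made after the BLQ results are known would look data-driven.
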